12.1.4 Medication errors

A medication error concerning trial products is defined as:

- Administration of wrong drug or use of wrong device. Note: Use of wrong DUN is not considered a medication error
- Wrong route of administration, such as intramuscular instead of s.c.
- Administration of an overdose with the intention to cause harm, misuse or abuse of trial product
- Accidental administration of a lower or higher dose than intended. That is a dose lower or higher than 0.6, 1.2, 1.8, 2.4 and 3.0 mg respectively (within 24 hours). However, the administered dose must deviate from the intended dose to an extent where clinical consequences for the trial subject were likely to happen as judged by the investigator, although they did not necessarily occur

If the subject discontinues trial product prematurely, this should not be reported as a medication error.

Medication errors must be reported on an AE form and a specific event form for medication error (see Section [8.4.3.1](#)).

12.1.5 Adverse events requiring additional data collection

AEs requiring additional data collection are AEs where the additional data will benefit the evaluation of the safety of the trial product.

The below lists AEs that require completion of specific event forms in the eCRFs (see Section [8.4.3.2](#)):

- Acute gallstone disease
- Neoplasm
- Pancreatitis
- Hepatic event (suspicion of DILI)
- Depression, suicidal ideation/behaviour

For details of these events, see Section [8.8](#).

12.1.6 Technical complaints

A technical complaint is any written, electronic, or oral communication that alleges product (medicine or device) defects. The technical complaint may be associated with an AE, but does not concern the AE itself.

Examples of technical complaints:

- The physical or chemical appearance of trial products (e.g., discoloration, particles or contamination)
- All packaging material including labelling
- Problems related to devices (e.g., to the injection mechanism, dose setting mechanism, push button or interface between the pen and the needle)

12.2 Reporting of adverse events

All events meeting the definition of an AE must be collected and reported. This includes events from the first trial-related activity after the subject has signed the informed consent until the end of the post-treatment follow-up period (30 days). The events must be recorded in the applicable eCRF forms in a timely manner, see timelines below in [Figure 12-1](#).

During each contact with the trial site staff, the subject must be asked about AEs and technical complaints, for example, by asking: “Have you experienced any problems since the last contact?”

In addition, the subject should be asked about the mood for example – ‘How has your mood been since the last contact?’

All AEs, observed by the investigator or subject, must be reported by the investigator and evaluated.

All AEs must be recorded by the investigator on an AE form. The investigator should report the diagnosis, if available. If no diagnosis is available, the investigator should record each sign and symptom as individual AEs using separate AE forms.

For SAEs, a safety information form must be completed in addition to the AE form. If several symptoms or diagnoses occur as part of the same clinical picture, one safety information form can be used to describe all the SAEs.

For all non-serious AEs, the applicable forms should be signed when the event is resolved or at the end of the trial at the latest.

[figure not shown]
Timelines for initial reporting of AEs

The investigator must complete the following forms in the eCRF within the specified timelines:

- **SAEs:** The AE form **within 24 hours** and the safety information form **within 5 calendar** days of the investigator's first knowledge of the SAE. Both forms must be signed **within 7 calendar days** from the date the information was entered in the eCRF.
- **For SAEs requiring reporting on a specific event form:** In addition to the above, the specific event form must be completed and signed within **14 calendar days** from the investigator's first knowledge of the AE.

If the eCRF is unavailable, the concerned AE information must be reported on a paper AE form and sent to Novo Nordisk by fax, e-mail or courier within the same timelines as stated above. When the eCRF becomes available again, the investigator must enter the information on the form into the eCRF.

Contact details (fax, telephone, e-mail and address) are provided in the investigator trial master file.

Timelines are for the completion of forms from the time of investigator's awareness.
AEs requiring specific event forms are described in Section 12.1.4 and 12.1.5.

AE: Adverse Event SIF: Safety Information form

Figure 12–1 Reporting of AEs

Novo Nordisk assessment of AE expectedness

Novo Nordisk assessment of expectedness is performed according to the following reference document: Company Core Data Sheet (CCDS), current version and any updates thereto.

Reporting of trial product-related SUSARs by Novo Nordisk

Novo Nordisk will notify the investigator of trial product-related suspected unexpected serious adverse reactions (SUSARs) in accordance with local requirements and ICH GCP ¹. In addition, the investigator will be informed of any trial-related SAEs that may warrant a change in any trial procedure.

In accordance with regulatory requirements, Novo Nordisk will inform the regulatory authorities, including EMA, of trial product-related SUSARs. In addition, Novo Nordisk will inform the IRBs/IECs of trial product-related SUSARs in accordance with local requirement and ICH GCP ¹, unless locally this is an obligation of the investigator.

Novo Nordisk products used as concomitant medication

If an AE is considered to have a causal relationship with a Novo Nordisk marketed product used as concomitant medication in the trial, it is important that the suspected relationship is reported to

Novo Nordisk (e.g. in the alternative aetiology section on the safety information form). Novo Nordisk may need to report this adverse event to relevant regulatory authorities.

12.3 Follow-up of adverse events

The investigator must record follow-up information by updating the forms in the eCRF.

Follow-up information must be reported to Novo Nordisk according to the following:

- **SAEs:** All SAEs must be followed until the outcome of the event is “recovered/resolved”, “recovered/resolved with sequelae” or “fatal”, and until all queries have been resolved. Cases of chronic conditions, cancer or AEs ongoing at time of death (where death is due to another AE) may be closed with the outcome “recovering/resolving” or “not recovered/not resolved”. Cases can be closed with the outcome of “recovering/resolving” when the subject has completed the follow-up period and is expected by the investigator to recover.

The SAE follow-up information should only include new (e.g., corrections or additional) information and must be reported **within 24 hours** of the investigator’s first knowledge of the information. This is also the case for previously non-serious AEs which subsequently become SAEs.

- **Non-serious AEs:** Non-serious AEs must be followed until the outcome of the event is “recovering/resolving”, “recovered/resolved” or “recovered/resolved with sequelae” or until the end of the follow-up period stated in the protocol, whichever comes first, and until all queries related to these AEs have been resolved. Cases of chronic conditions, cancer or AEs ongoing at time of death (where death is due to another AE) may be closed with the outcome “recovering/resolving” or “not recovered/not resolved”. Cases can be closed with the outcome of “recovering/resolving” when the subject has completed the follow-up period and is expected by the investigator to recover.

The investigator must ensure that the recording of the worst case severity and seriousness of an event is kept throughout the trial. A worsening of an unresolved AE must be reported as follow up with re-assessment of severity and/or seriousness of the event.

Queries or follow-up requests from Novo Nordisk must be responded to **within 14 calendar days** from the date of receipt of the request, unless otherwise specified in the follow-up request.

SAEs after end of trial: If the investigator becomes aware of a SAE with a suspected causal relationship to the investigational medicinal product occurring to a subject after the subject has ended the trial, the investigator should report this SAE within the same timelines as for SAEs during the trial.

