12.1 Definitions

12.1.1 Adverse event

An adverse event (AE) is any untoward medical occurrence in a subject administered a medicinal product, and which does not necessarily have a causal relationship with this treatment.

An AE can therefore be any unfavourable and unintended sign (including an abnormal laboratory finding), symptom or disease temporally associated with the use of a product, whether or not considered related to the product.

An AE includes:

- A clinically significant worsening of a concomitant illness.
- A CLAE: a clinical laboratory abnormality which is clinically significant, i.e., an abnormality that suggests a disease and/or organ toxicity and is of a severity that requires active management. Active management includes active treatment or further investigations, for example, change of medicine dose or more frequent follow-up due to the abnormality.

The following should **not** be reported as AEs:

- Pre-existing conditions, including those found as a result of screening or other trial procedures performed before exposure to trial product (pre-existing conditions should be reported as medical history or concomitant illness).
- Pre-planned procedures unless the condition for which the procedure was planned has worsened from the first trial-related activity after the subject has signed the informed consent.
- Non-serious hypoglycaemia is an AE, but is reported on a hypoglycaemic episode form instead of an AE form [8.4.4](#)

The following three definitions are used when assessing an AE:

- **Severity**
 - **Mild** – no or transient symptoms, no interference with the subject's daily activities.
 - **Moderate** – marked symptoms, moderate interference with the subject's daily activities.
 - **Severe** – considerable interference with the subject's daily activities; unacceptable.
- **Causality**

Relationship between an AE and the relevant trial product(s):

- **Probable** - Good reason and sufficient documentation to assume a causal relationship.
- **Possible** - A causal relationship is conceivable and cannot be dismissed.
- **Unlikely** - The event is most likely related to aetiology other than the trial product.

- **Final outcome**

- **Recovered/resolved** - The subject has fully recovered, or by medical or surgical treatment, the condition has returned to the level observed at the first trial-related activity after the subject signed the informed consent.

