2.4.3.2 Safety endpoints

Descriptive statistics for all safety endpoints will be provided with the aim to compare liraglutide 3.0 mg and placebo. All analyses and tabulations will be done using the safety analysis set. Unless otherwise stated, no formal statistical analyses are planned for the safety endpoints.

Adverse events and hypoglycaemic episodes will be classified and analysed as ‘in trial’ and ‘on drug’ defined in terms of patient years of observation (PYO) and patient years of exposure (PYE), respectively. For each subject PYO is defined as number of days from date of randomisation until and including date of follow-up visit or date of last contact. For each subject PYE is defined as time intervals of exposure to trial drug including an ascertainment window of 14 days for each exposure interval.

Adverse events

AEs will be coded using the current version of Medical Dictionary for Regulatory Activities (MedDRA). All AEs will be presented based on system organ class, high level group term and preferred terms.

AEs, which occurred while the subject was in trial or on drug will be summarised descriptively, whereas AEs, which occurred before first exposure to trial drug or after the follow-up visit will only be presented in listings. AEs will be displayed in terms of the number of subjects with at least one event (N), the percentage of subjects with at least one event (%), the number of events (E) and the event rate per 100 years (R). Furthermore, AEs will be summarised by seriousness, severity, relation to trial drug, premature treatment discontinuation due to AE and outcome.

Summary tables by system organ class, high level group term and preferred term will be made for all AEs, SAEs, AEs possibly or probably related to trial drug, severe AEs, AEs occurring in at least 5% of the subjects in any arm, and AEs occurring in at least 1% of the subjects in any treatment arm.

AEs requiring completion of specific event forms will be presented in tables and listings. In addition, time to occurrence of these AEs will be presented in cumulative incidence plots.

Hypoglycaemic episodes

All hypoglycaemic episodes will be summarised in terms of N, %, E, rate as on drug (PYE) and in trial (PYO) and using same ascertainment window of 14 days as for AEs.

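### An AE that starts before the first dose and turns severe or serious on drug is, if classified by onset, left out of the AE and SAE summary tables

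*Protocol*

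**What the plan says.** Collection starts before dosing. Protocol 12.2 requires sites to report "events from the first trial-related activity after the subject has signed the informed consent", through to the end of the 30-day follow-up.

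Protocol 12.3 sets the rule for an AE that gets worse: "A worsening of an unresolved AE must be reported as follow up with re-assessment of severity and/or seriousness of the event". It adds: "The investigator must ensure that the recording of the worst case severity and seriousness of an event is kept throughout the trial". A change from non-serious to serious is also treated as follow-up information, due within 24 hours: "This is also the case for previously non-serious AEs which subsequently become SAEs".

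SAP 2.4.3.2, repeating Protocol 17.4.2.2, divides events between tables and listings. On one side, "AEs, which occurred while the subject was in trial or on drug will be summarised descriptively". On the other, "AEs, which occurred before first exposure to trial drug or after the follow-up visit will only be presented in listings". The tables are described thus: "Summary tables by system organ class, high level group term and preferred term will be made for all AEs, SAEs", and the list goes on to related AEs, severe AEs and AEs above two frequency cut-offs.

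Illness that predates the trial follows another rule. Protocol 12.1.1 counts as an AE "A clinically significant worsening of a concomitant illness", and Protocol 8.2.4 says the same.

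**The concern.** Each rule is ordinary taken alone. The trouble comes from combining them. Section 12.3 ties the worst severity and seriousness to a record whose onset precedes dosing, and the SAP keeps pre-exposure events out of the tables. An event that the drug may have aggravated would then not enter the comparison between arms, although it is the worsening on drug that makes it informative.

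The two worsening rules also point in opposite directions. On-drug deterioration of a complaint present at screening counts as an AE. The same deterioration of a complaint that began a few days later, still before any dose, does not. SAE and severe-AE tables usually rest on small counts, so even a few such events could be visible there.

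**Working it through.** No figure in the plan bears on this and no power or sample-size calculation enters. The check is to follow one event through the rules, then look for text that would change the outcome.

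**Trace.** A subject develops a new mild complaint after the screening visit. It is unresolved at first dose and becomes severe or serious on drug.

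1. It is collected as an AE (Protocol 12.2).
2. When it worsens, the existing record is updated and no second AE is created (Protocol 12.3).
3. Its onset precedes first exposure, so on an onset classification it goes to listings only (SAP 2.4.3.2; Protocol 17.4.2.2).

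**The same worsening, by when the complaint began**

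| Complaint began | Record when it worsens on drug | Where it appears |
|---|---|---|
| Present at the screening visit | Reported as an AE (Protocol 8.2.4, 12.1.1) | Tables |
| After screening, before first dose | Existing AE updated (Protocol 12.3) | Listings only |
| After first dose | Existing AE updated, worst severity and seriousness kept (Protocol 12.3) | Tables |

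Only the middle row loses the event.

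**Does other text close the gap?**

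- Neither document defines a treatment-emergent AE. The one treatment-emergent rule, in the hypoglycaemia part of SAP 2.4.3.2, goes by onset and has no clause for worsening.
- Neither document asks for a date of worsening. The eCRF audit trail in Protocol 13.1 dates the data entry, not the clinical change.
- Protocol Amendments 1 to 3 and SAP 3.1 and 3.2 leave these rules as they are.
- SAP 2.4.3.2 starts patient years of observation at randomisation. An AE between randomisation and first dose is therefore both in trial and before first exposure, and the two allocation rules conflict for it. This also shows that the dating of AEs needs stating.

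**Size.** A count would need the AE rate before dosing and the share of those AEs that are unresolved and later worsen. The documents give neither. They do show how short the window is. The flow chart puts screening one week before randomisation. Treatment plus follow-up is 56 weeks + 30 days = 56 + 30/7 = 60.3 weeks. The ratio is 1/60.3 = 1.7% of the post-randomisation time of a subject who completes. It would be 2/60.3 = 3.3% if the seven-day visit window were read as a further week. This describes time at risk of falling into the gap; it is not an estimate of events.

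**The case against.** The strongest objection is that the SAP says *occurred*, not *began*, and does not define the word for AEs, so exclusion is an inference and not a written rule. That is correct. Onset is nevertheless the natural reading and the one the SAP uses for hypoglycaemia. If another reading is intended, the date needed to apply it is not specified.

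It is also fair that few events are likely, that they remain in the listings and that SAE reporting is untouched. Worsening from mild to moderate falls in the same class, so not every such event is severe or serious. Events found through a trial procedure before exposure count as concomitant illness under Protocol 8.2.4, which narrows the class further. All of this limits the size of the point but leaves the mechanism in place.

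Three stronger readings are tempting, and the documents do not support them.

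- *Gastrointestinal complaints present mildly at entry would be lost when they worsen during escalation.* Illness present at the screening visit is a concomitant illness. Its clinically significant worsening is reported as an AE and so reaches the tables.
- *Events around drug stops and restarts vanish in the same way.* AEs are summarised in trial as well as on drug, so an event starting in an off-drug gap stays in the in-trial tables with its worst severity. Each exposure interval also carries a 14-day ascertainment window, which brings part of these events into the on-drug tables. An event that begins on drug and turns serious after stopping is likewise tabulated, not missing.
- *The on-drug tables are the main safety comparison.* Neither document ranks the on-drug period above the in-trial period.

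**Conclusion.** The point holds in a narrow form. For AEs that arise between consent and first dose, are unresolved at first dose and worsen on drug, the recording rule and the tabulation rule together remove the event from the all-AE, SAE, severe-AE and related-AE tables. This treats them differently from worsening of illness present at screening, and the documents give no reason for the difference.

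The conclusion rests on one assumption, that AEs are allocated by onset. The number affected cannot be computed from the documents and is probably small. The consequence is confined to the summary tables and does not touch the efficacy analyses. It is a small tabulation error that is cheap to remove.

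**What to change.** In Protocol 12.3, require that an increase in severity or seriousness after first exposure, in an AE that began before first exposure, be reported as a new AE. Alternatively, keep the single record and add the date of worsening. In SAP 2.4.3.2, state that such an AE is tabulated as in trial or on drug from the date of worsening, and say how an AE between randomisation and first dose is allocated.

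A new record does not count the episode twice in the tables, provided the pre-exposure record stays in listings only. The cost is about one sentence in each document, possibly one date field on the AE form, and a few more AEs in the counts.

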12.4 Technical complaints and technical complaint samples

12.4.1 Reporting of technical complaints

All technical complaints on any of the following products:

- Liraglutide 6 mg/ml, 3 ml PDS290 pen-injector
- Placebo PDS290 pen-injector
- Novo Nordisk needles for pen-injector

which occur from the time of first usage of the product until the time of the last usage of the product, must be collected and reported to Customer Complaint Center, Novo Nordisk.

Contact details (fax, e-mail and address) are provided in [Attachment I](#) to the protocol.

The investigator must assess whether the technical complaint is related to any AEs and/or SAEs.

Technical complaints must be reported on a separate technical complaint form:

- One technical complaint form must be completed for each affected DUN
- If DUN is not available, a technical complaint form for each code or lot number must be completed

The investigator must complete the technical complaint form in the eCRF within the following timelines of the trial site obtaining knowledge of the technical complaint:

- Technical complaints **within 5 calendar days**
- Technical complaint assessed as related to an SAE **within 24 hours**

If the eCRF is unavailable or when reporting a technical complaint that is not subject related, the information must be provided on a paper form by fax, e-mail or courier to Customer Complaint Center, Novo Nordisk, within the same timelines as stated above. When the eCRF becomes available again, the investigator must enter the information on the technical complaint form in the eCRF.

12.4.2 Collection, storage and shipment of technical complaint samples

The investigator must collect the technical complaint sample and notify the monitor **within 5 calendar days** of obtaining the sample at trial site. The monitor must coordinate the shipment to Customer Complaint Center, Novo Nordisk (the address is provided in [Attachment I](#)) and ensure that the sample is sent as soon as possible. A copy of the technical complaint form must be included in the shipment of the sample. If several samples are returned in one shipment, the individual sample and the corresponding technical complaint form must be clearly separated.

The investigator must ensure that the technical complaint sample contains the code or lot number, and, if available, the DUN. All parts of the DUN should be returned.

If the technical complaint sample is unobtainable, the investigator must specify on the technical complaint form why it is unobtainable.

Storage of the technical complaint sample must be done in accordance with the conditions prescribed for the product.

12.5 Pregnancies

12.5.1 Pregnancies in female subjects

Female subjects must be instructed to notify the investigator immediately if they become pregnant during the trial. The investigator must report any pregnancy in subjects who have received trial product(s).

The investigator must follow the pregnancy until the pregnancy outcome and the newborn infant is one month of age.

The investigator must report information about the pregnancy, pregnancy outcome, and health of the newborn infant(s), as well as AEs in connection with the pregnancy, and AEs in the foetus and newborn infant.

The following must be collected and reported by the investigator to Novo Nordisk electronically (e.g., in PDF format), or by fax or courier:

1. Reporting of pregnancy information

Information about the pregnancy and pregnancy outcome/health of the newborn infant(s) has to be reported on Maternal Form 1A and 1B, respectively.

When the pregnancy outcome is abnormal (i.e., congenital anomalies, foetal death including spontaneous abortion and/or any anomalies of the foetus observed at gross examination or during autopsy), and/or when a congenital anomaly is diagnosed within the first month, further information has to be reported for the female subject on Maternal Form 2. In addition, information from the male partner has to be reported on the Paternal Form, after an informed consent has been obtained from the male partner.

Initial reporting and follow-up information must be reported **within 14 calendar days** of the investigator's first knowledge of initial or follow-up information.

2. Reporting of AE information

The investigator has to report AEs in connection with the pregnancy as well as in the foetus and new born infant(s). The SAEs that must be reported include abnormal outcome, such as foetal death (including spontaneous abortion), and congenital anomalies (including those observed at gross examination or during autopsy of the foetus), as well as other pregnancy complications fulfilling the criteria of a SAE.

Forms and timelines for reporting AEs:

Non-serious AEs:

- AE form within 14 calendar days of the investigator's first knowledge of the initial or follow-up information to the non-serious AE.

Serious AEs:

- AE form within 24 hours of the investigator's first knowledge of the SAE.
- Safety information form within 5 calendar days of the investigator's first knowledge of the SAE.
- SAE follow-up information to the AE form and/or safety information form within 24 hours of the investigator's first knowledge of the follow-up information.

^a It must be clearly stated in the AE diagnosis field on the AE form if the event occurred in the subject, foetus or new born infant. If the AE occurred in the foetus or new born infant, the AE can only be reported on paper AE and safety information form.

Any queries or follow-up requests from Novo Nordisk to non-serious AEs, SAEs and pregnancy forms must be responded to by the investigator **within 14 calendar days** from the date of receipt of the request, unless otherwise specified in the follow-up request.

